### **8.3.11 Pregnancy**

Female patients will be instructed to notify the investigator immediately if they become pregnant from the signing of informed consent until 30 days following the final dose of study drug. Male patients will be instructed to notify the investigator immediately if their partner becomes pregnant. Pregnant patients will be withdrawn from further study treatment. The patients will also be instructed to report pregnancies discovered after the last visit, if they believe that conception occurred during their participation in the study.

A pregnancy as such is not an AE, unless there is a possibility that the IMP has interfered with the efficiency of any contraceptive measures. However, the investigator should report

pregnancies according to the procedures and timelines described for reporting of SAEs (Section 8.2.5). The pregnancy report form should be used instead of the SAE form.

The pregnant patient or pregnant partner will be followed until the end of the pregnancy. Any complication during the pregnancy should preferably be reported as an AE. The outcome of the pregnancy must be reported on the pregnancy report form. Any spontaneous abortion, stillbirth, birth defect/congenital anomaly, death, or other serious infant condition must be reported and followed up as an SAE.

#### **8.3.12 *Protocol Deviations Due to an Emergency or Adverse Event***

In the case of an emergency or AE, departures from the protocol may be necessary. Such protocol deviations will be determined as allowable on a case-by-case basis. The investigator or other physician in attendance in such an emergency must contact the Medical Monitor as soon as possible to discuss the circumstances of the emergency. The Medical Monitor and the investigator will confer to decide whether the patient should continue to receive study medication. All protocol deviations and the reasons for such deviations must be noted in the eCRF.

---

## 9. STATISTICAL METHODS

### 9.1 General Statistical Methods

In general, data will be summarized by means of summary statistics. Continuous data will be presented with the number of observations, mean value, confidence intervals, standard deviation, minimum, Q1, median, Q3 and maximum value. Change from baseline to each post-baseline visit will be also described using descriptive statistics. Categorical data will be presented as counts and percentages.

The data will be presented for each treatment group by visit.

Individual patient data will be listed for all enrolled patients. Listings will be sorted by center and patient number and labelled by randomized treatment group.

Before unmasking the study data, a separate statistical analysis plan (SAP), which will provide the technical details of the statistical analysis outlined below, will be prepared and approved.

For statistical analyses, the following definitions will be applied:

- Baseline: Baseline is defined as Visit 1 (Day 1, 24 h after the cataract surgery).
- Randomized treatment group: The treatment that was assigned at the time of randomization.

The assessments performed at Visit 1 (Day 1) will be considered the baseline values.

All data collected during study follow-up will be displayed and analyzed according to the actual visit data in the eCRF.

Unless otherwise stated, all statistical tests will be conducted using two-sided alpha = 0.05.

#### 9.1.1 *Sample Size*

A two group  $\chi^2$  test with a 0.05 two-sided significance level will have 80% power to detect the difference between a proportion with complete resolution of anterior chamber cells in the active group of 0.22 and the placebo group proportion of 0.07 (odds ratio of 3.747) when the sample size is 202. Considering a 4% lost to follow-up rate a final sample size of 210 patients will be required (140 clobetasol, 70 placebo, in a 2:1 randomization ratio).

#### 9.1.2 *Interim Analyses*

An interim analysis is not planned for this study.

#### 9.1.3 *Missing, Unused, and Spurious Data*

Any missing, unused, or spurious data will be noted in the final clinical study report (CSR) and presented in the data listings.

#### 9.1.4 *Analysis Populations*

Analysis will include the following populations:

- **Full Analysis Set (FAS):** The FAS will be the primary analysis set for the efficacy endpoints and will include all randomized patients. The FAS population will be analyzed according to the planned treatment.

- **Safety Population:** The safety set will be the primary analysis set for the safety endpoints and will include all randomized patients who took at least one dose of IMP. The safety set will be analyzed according to the treatment actually received.
- **Per Protocol (PP) Population:** The PP population set will be tested to confirm the robustness of the efficacy analyses and will include all patients in the FAS who have no major protocol deviations (i.e. patients who comply the protocol sufficiently to ensure that the data exhibits the effects of the IMP when administered as intended). Protocol violations include: violations of entry criteria, lack of compliance and the use of prohibited medication. The PP population will be analyzed according to the treatment actually received.

Efficacy analyses will be based on both the FAS and the PP, but the FAS will be considered the primary analysis population.

Safety analyses will be based on the safety set.

#### **9.1.5 Patient Disposition**

The numbers of patients in each treatment group who completed the study and who terminated early will be tabulated. For patients who terminated early, primary and secondary reasons for termination will be tabulated. Patients who were excluded from each of the study populations defined in Section [9.1.4](#), and their reasons for exclusion, will be listed.

#### **9.1.6 Demographics and Baseline Characteristics**

Patient disposition, demographic and other baseline data will be summarized by randomized treatment group. Both the FAS and PP will be used for this presentation.

Frequency tables for medical history will present the percentage of patients per SOC and PT.

#### **9.1.7 Protocol Deviations**

Protocol deviations are defined as violations from the procedures outlined in the protocol. **Major** protocol deviations are protocol violations likely to affect the study results and leading to the exclusion of the patient from the MPP.

Once the database has been completed and considered as “clean”, a data masked review will be conducted before the database lock in order to identify all major protocol violations and assign patients into each of the analysis sets as defined in Section [9.1.4](#).

Patients with protocol deviations will be presented in the data listings. Protocol violations will be tabulated by treatment group and violation.

The protocol deviations are considered critical (or very serious) and major (or severe), according to the following definitions:

- **Critical or very serious:** Deviations affecting / they have adversely affected the rights, safety or welfare of patients and / or the quality and integrity of data
- **Major or serious:** Deviations that may affect / have adversely affected the rights, safety or welfare of patients and / or the quality and integrity of data.

The Sponsor or designee will report the protocol deviations to the Health Authorities according to local rules and regulations.

### **9.1.8 Compliance with Study Medication**

Duration of treatment and treatment compliance will be presented for the FAS population by randomized treatment group using summary statistics.

### **9.1.9 Concomitant Medications**

Prior and concomitant treatment will be coded according to WHO Drug Dictionary.

Concomitant medication and concomitant therapy will be summarized for the FAS population by randomized treatment group as percentage of patients being treated with each type of medication/therapy classified according to Anatomical Therapeutic Chemical (ATC) level 2 (therapeutic main group) and ATC level 3 (pharmacological subgroup).

Prior treatment will be summarized the same way as concomitant treatment.

### **9.1.10 Primary Analysis**

The aim of the primary analysis of this study is to assess the superiority of clobetasol propionate ophthalmic nanoemulsion 0.05% compared to placebo with respect to the primary endpoint in the FAS.

The primary analysis will be based on a single study eye for each patient. Each patient's study eye will be defined as the surgery eye.

The test will be the proportion of study eyes with complete clearing of anterior chamber cells (count cell = 0) at Visit 3 (Day 8 ± 1 day) without receiving rescue medication as compared between clobetasol propionate ophthalmic nanoemulsion 0.05% dosed QID and placebo dosed QID using the chi square statistic.

The PP population set will be also tested to confirm the robustness of the primary analysis.

The primary estimand (efficacy estimand) will be defined as the effect of the randomized treatments in all subjects meeting selection criteria assuming continuation of randomized treatments for the duration of the study regardless of actual compliance.

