	
IMP when administered as intended). Protocol violations include: violations of entry criteria, lack of compliance and the use of prohibited medication. The PP population will be analyzed according to the treatment actually received.
 
Efficacy analyses will be based on both the FAS and the PP, but the FAS will be considered the primary analysis population.
 
Safety analyses will be based on the safety set.
 
Summary statistics
 
In general, data will be summarized by means of summary statistics. Continuous data will be presented with the number of observations, mean value, confidence intervals, standard deviation, minimum, Q1, median, Q3 and maximum value. Change from baseline to each post-baseline visit will be also described using descriptive statistics. Categorical data will be presented as counts and percentages.
 
The data will be presented for each treatment group by visit.
 
Individual patient data will be listed for all enrolled patients. Listings will be sorted by center and patient number and labelled by randomized treatment group.
 
Missing data
 
Data not collected after rescue therapy has been initiated will not be considered missing since the primary measure is a responder measure where rescue is considered treatment failure. Patients with missing data for the analysis of the primary endpoint will be assigned the status of treatment failure.
 
Primary analysis
 
The aim of the primary analysis of this study is to assess the superiority of clobetasol propionate ophthalmic nanoemulsion 0.05% compared to placebo with respect to the primary endpoint in the FAS.
 
The primary analysis will be based on a single study eye for each patient. Each patient's study eye will be defined as the surgery eye.
 
The test will be the proportion of study eyes with complete clearing of anterior chamber cells (count cell = 0) at Visit 3 (Day 8 ± 1 day) without receiving rescue medication as compared between clobetasol propionate ophthalmic nanoemulsion 0.05% dosed QID and placebo dosed QID using the chi square statistic.
 
The PP population set will be also tested to confirm the robustness of the primary analysis.
 
Key Secondary Analysis
 
The aim of the key secondary analysis of this study is to assess the superiority of clobetasol propionate ophthalmic nanoemulsion 0.05% compared to placebo with respect to the key secondary endpoint in the FAS.
 
The key secondary analysis will be based on a single study eye for each patient. Each patient's study eye will be defined as the surgery eye.

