### 5.3 **Withdrawal, Premature Discontinuation of Study Medication, and Replacement of Patients**

Patients are free to discontinue their participation in the study at any time. Additionally, patients may be withdrawn from study at any time, if deemed necessary by the investigator

(after discussion with the Medical Monitor). Withdrawal from the study will not affect or prejudice the patients' further care or treatment.

Potential reasons for withdrawal of patients from this study are:

- The decision of a patient to withdraw informed consent
- Patient is lost to follow-up (Section [5.3.1](#))
- Potential reasons for premature discontinuation of study medication include, but are not limited to: Occurrence of a treatment-emergent AE (TEAE) or considerable worsening of an AE that, in the opinion of the investigator in consultation with the Medical Monitor and Sponsor, represents an unacceptable risk to the patient if he/she continues to receive study medication. The investigator must follow the patient until the AE resolves or satisfactorily stabilizes
- Administration of a rescue medication. Any patient placed on rescue therapy will discontinue the use of the IMP (see Sections [6.7.1](#) and [6.7.2](#))
- Patient's failure to comply with protocol requirements or study related procedures
- In case of pregnancy. The investigator will continue the follow-up of the patient until the end of the pregnancy
- Any surgery (different from the actual routine cataract surgery on the study eye) in the study or contralateral eye

In any case of premature discontinuation of study medication, the investigator must make extensive efforts to ensure that the patient will attend all his/her remaining study visits until study completion (at Visit 5), aiming to collect the most complete efficacy and safety data.

The reason and date the patient is withdrawn from the study will be documented in the eCRF (e.g. lost to follow-up, consent withdrawn, AEs, etc.).

If a patient is withdrawn from the study, the investigator should attempt to complete all discharge procedures (including the Early Termination Visit; Section [4.3.2.8](#)). All AEs should be followed up according to Section [8.3.6](#).

If a patient is withdrawn from the study, or withdraw his/her consent, all data collected until the time of withdrawal will be used in the analyses, unless this is prohibited by local regulations.

Patients who drop out from the study will not be replaced.

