### 6.7.2 Rescue Medication

Any patients not responding adequately to the IMP may be rescued and placed on alternate therapy (Section [6.7](#)) at the investigator's discretion at any time.

The choice of rescue medication is at the investigator's discretion. Any patient placed on rescue therapy will discontinue the use of the IMP and the investigator must make extensive efforts to ensure that the patient will attend all his/her remaining study visits until study completion, aiming to collect the most complete efficacy and safety data.

Additionally, patients will be asked to phone the study center at any time to speak to a member of the medical personnel should they experience any worsening of ocular conditions or other AEs.

Rescued patients will be considered treatment failures, but the need for rescue therapy will not be considered an AE.

---

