### 6.3.7 Sensitivity Analysis

Sensitivity analysis will be carried out for possible intercurrent events such as discontinuation due to AE, lack of efficacy and use of rescue and prohibited medication. New estimands associated to each intercurrent event will be added to the already existing primary estimand accordingly.

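### The stated primary estimand assumes continued treatment, but the primary test is a rescue-as-failure composite, and the SAP leaves rescue and missing-data handling unsettled

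*Protocol*

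**What the plan says.** **Estimand.** Protocol 9.1.10 takes the primary estimand to be the effect of the randomized treatments in all eligible subjects, "assuming continuation of randomized treatments for the duration of the study regardless of actual compliance".

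**Primary test.** The same section compares the arms by chi-square on the proportion of study eyes meeting the condition "count cell = 0) at Visit 3 (Day 8 ± 1 day) without receiving rescue medication". SAP 6.3.5 repeats this condition.

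**Rescue.** The missing-data paragraph of the Protocol synopsis says "the primary measure is a responder measure where rescue is considered treatment failure". Protocol 6.7.2 agrees: "Rescued patients will be considered treatment failures". Under Protocol 5.3, "Any patient placed on rescue therapy will discontinue the use of the IMP".

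**Missing data.** The synopsis says "Patients with missing data for the analysis of the primary endpoint will be assigned the status of treatment failure". Protocol 9.1.3 does not repeat this rule and provides only for noting and listing missing data. SAP 6.6 foresees no imputation.

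**Which visits count.** SAP section 5 restricts FAS efficacy analyses to visits on study treatment and free of prohibited or rescue medication. The same section, like Protocol 9.1.4, defines the FAS as all randomized patients.

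**Sensitivity.** SAP 6.3.7 says "New estimands associated to each intercurrent event will be added to the already existing primary estimand accordingly". It defines none of the new estimands and does not restate the existing one.

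**The concern.** An estimand sentence fixes what the primary result may be said to measure. Here it points to the effect had everyone stayed on randomized treatment. Rescued patients must stop the study product, so for them continued treatment is counterfactual and their outcome under it would have to be modelled. The plan instead sets rescue to failure, which answers another question: how often does a patient assigned to each arm clear by Day 8 without needing rescue?

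Two things are at stake. One is interpretation: the stated target and the reported difference are different quantities, and the undefined sensitivity estimands are to be added to that target. The other is who is counted. The synopsis puts a rescued or missing patient in the denominator as a failure, whereas SAP sections 5 and 6.6, read literally, leave that patient out. If this is not settled before unmasking, the choice could be made with results in view.

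**Working it through.** **The plan's own figure.** Inputs from Protocol 9.1.1: 0.22 active, 0.07 placebo, 2:1 allocation, two-sided 0.05, 80% power. The pooled rate is (0.07 + 2 × 0.22)/3 = 0.17. The placebo sample size from the pooled-variance formula is

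[1.960 × √(0.17 × 0.83 × 1.5) + 0.842 × √(0.07 × 0.93 + 0.22 × 0.78/2)]² / 0.15² ≈ 67.1.

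Three times this is 201.3, so 202 in total (204 if each arm is rounded up). Power at 202 is 0.802. The odds ratio is (0.22/0.78)/(0.07/0.93) = 3.747, and 202/0.96 = 210.4 against the planned 210. These figures reproduce and are not in dispute.

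**Possible readings of the estimand sentence against the test.**

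| Reading | Day 8 status of a rescued patient | Matches the test? |
|---|---|---|
| Hypothetical (treatment continued) | Outcome had treatment continued, to be estimated | No; no method planned |
| Treatment policy (regardless of compliance) | Cell grade actually observed after rescue | No |
| Composite | Failure | Yes, but this is not what the sentence says |

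**Size.** The documents give no rescue rate and do not say which quantity 0.22 and 0.07 represent, so both cases are shown. All event rates below are assumptions.

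*Case A: 0.22 and 0.07 are composite rates.* Assume rescue in 10% of active and 30% of placebo patients. Hypothetical rate = composite rate + (proportion rescued × proportion of them who would have cleared).
- Non-rescued patients clear at 0.22/0.90 = 24.4% on active and 0.07/0.70 = 10.0% on placebo.
- If rescued patients would have cleared at the same rate as the others in their arm, the hypothetical difference is 24.4 − 10.0 = 14.4 points, against 15.
- At half that rate: 0.22 + 0.10 × 0.122 = 0.232 and 0.07 + 0.30 × 0.05 = 0.085, a difference of 14.7 points.
- If none would have cleared, the two effects coincide at 15 points.

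*Case B: 0.22 and 0.07 are continued-treatment rates.* Assume that patients with rescue or missing data would have cleared like the others in their arm. Composite rate = rate × (1 − event proportion). The continued-treatment difference is 15.0 points.

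| Events, active/placebo | Composite rates | Difference (points) |
|---|---|---|
| 20%/20% | 0.176, 0.056 | 12.0 |
| 10%/10% | 0.198, 0.063 | 13.5 |
| 4%/4% | 0.211, 0.067 | 14.4 |
| 5%/20% | 0.209, 0.056 | 15.3 |
| 5%/30% | 0.209, 0.049 | 16.0 |

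**Leaving these patients out, as SAP sections 5 and 6.6 read literally.** Under Case B's assumption, exclusion recovers 15 points. If instead none of these patients would have cleared, the composite and continued-treatment differences are both 15 points (power 0.82 with 140:70), and exclusion gives:
- 5%/20%: 0.22/0.95 − 0.07/0.80 = 0.232 − 0.088 = 14.4 points, power 0.66.
- 5%/30%: 0.22/0.95 − 0.07/0.70 = 0.232 − 0.100 = 13.2 points, power 0.51.
- 20%/20%: 0.22/0.80 − 0.07/0.80 = 0.275 − 0.0875 = 18.75 points, power 0.84.

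Exclusion therefore matches the stated estimand only if the events are unrelated to outcome. Protocol 6.7.2 provides rescue for inadequate response, which makes that hard to assume.

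**The case against.** The best defence is that the sentence is only loosely worded. Its compliance clause, with all randomized patients analysed as assigned, can be taken as an intention-to-treat statement in which rescue is handled inside the outcome. Both documents spell out the rescue-free condition, and the planned table title claims nothing about continued treatment. Different sensitivity targets are also intended, so a difference from the primary is no fault in itself.

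Much of this stands. Nothing in the documents says the result will be presented as an effect under continued treatment, and the fault in the sensitivity section is that its estimands are undefined. The defence does not remove the mismatch: the sentence expressly assumes continuation, and a treatment-policy reading would use post-rescue findings, not set them to failure.

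Three stronger readings are tempting but not supported:
- *The plan as a whole counts missing data as failure.* Only the synopsis says so; SAP 6.6 and section 5 point the other way.
- *The gap is as large as 4 points.* Adding 20% clearing among rescued patients in both arms to Case A gives 0.22 + 0.10 × 0.20 = 24% and 0.07 + 0.30 × 0.20 = 13%, a difference of 11 points. That requires rescued placebo patients to clear at twice the 10% rate of those who needed no rescue, and it shows movement in one direction only.
- *The primary test is invalid or the trial is under-sized.* A rescue-as-failure responder comparison is a legitimate superiority test, and the stated sample size reproduces.

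**Conclusion.** The point holds as a mismatch between the stated estimand and the planned estimator, together with unsettled handling of rescued, off-treatment and missing patients. It concerns what the result may be said to estimate and who is in the denominator. It does not overturn the superiority test.

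The size is uncertain and its direction is not fixed. In Case A the hypothetical difference is 14.4 points against a composite 15, with rescued patients clearing like the others in their arm. In Case B the composite difference runs from 12 to 16 points against 15. All of this rests on assumed event rates and on assumptions about what affected patients would have done. The mismatch itself follows from the text and needs none of them. The correction should be made, because the stated target is wrong as written and cheap to put right.

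**What to change.** Before unmasking:

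1. Replace the estimand sentence in Protocol 9.1.10, and state in SAP 6.3.5, a composite estimand: the difference between arms, in all randomized patients, in the proportion with study-eye cell grade 0 at Day 8 without prior rescue. Count rescue as non-response, and missing Day 8 data as non-response in line with the synopsis.
2. Name one analysis strategy for treatment discontinuation without rescue. Treatment policy is one option, since Protocol 4.1 and 5.3 already ask these patients to attend their remaining visits.
3. Amend SAP sections 5 and 6.6 so that they do not remove rescued, off-treatment or missing patients from the primary denominator.
4. In SAP 6.3.7, define each sensitivity estimand. Keep any continued-treatment version as a named one, with its estimation method and assumptions.

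The cost is a short Protocol amendment and SAP revision. Some patients whom SAP section 5 would leave out will be counted in the primary denominator. Data collection, the chi-square test and the sample size do not change.
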